#### Data Analysis

The analytic plan includes conducting an independent-group t-test of each of the following continuous dependent variables, or chi-square for categorical dependent variables: 1)

proportion drug-free urines; 2) retention in program (Chi-Square); 3) Quality of life score on the QOLI; 4) Delay discounting constant k; 5) Stop signal reaction time (SSRT) on the stop-signal task; 7) Reaction time in the Emotional Go-NoGo task, 8) errors in the DKEFS Tower Test.

A repeated-measures design will be used to examine the within-subjects effects of the treatments on state depression and quality of life, as well as for a group X treatment interaction effect. Although we do not expect an intervention of this time scale of to alter trait impulsivity, we will also analyze within-subject changes in BIS11 scores as an exploratory analysis. Lastly, a between-group design comparing the MFP group vs. TAU group for substance use primary outcomes of symptomology and neurobehavioral measures for problem solving and impulsivity. Individual differences in PTSD and anxiety measures and other symptomatology will be included as covariates to account for confounding factors in the analyses.

c. Facilities and Resources

The consent procedures and behavioral testing of this protocol will take place in the new second-floor Mental Health services facility at RICVAMC. Written informed consent procedures and clinical interviewing will take place in private interview rooms of this new second-floor RICVAMC wing. Questionnaires and laboratory behavioral tasks will be administered at dedicated research task workstations installed in testing rooms.

d. Staff Qualifications

*[name].* will be the Principal Investigator of this protocol. [name] has a 5/8 VA appointment and a joint (faculty) appointment as Associate Professor of Psychiatry at Virginia Commonwealth University. He has extensive experience in the laboratory testing of impulse control and decision-making in addicted inpatients, outpatients, and at-risk human subjects. He is also known for his successful design and execution of protocols to examine the neurocircuitry of motivation and self-control in addicted and adolescent at-risk populations. He has over 50 peer-reviewed publications and book chapters, 48 of which are available in PUBMED.

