**1. Purpose and Objectives:**

This protocol does not include any administration of medication or other interventions. This protocol will record cognitive performance and decision-making behavior in Veterans who seek mental health services in the substance use disorder intensive outpatient program (IOP). The goal is to identify the neurobehavioral effects of a structured, brief cognitive-based psychotherapy currently being conducted in the IOP along with other supportive, unstructured, treatments. The benefit of this study will be to obtain a better understanding of neurobehavioral changes occurring from evidence-informed treatments.

Aim 1: To determine if measurable neurobehavioral function in the domains of problem solving, decision making, and motoric impulsivity is predictive of treatment success and adherence outcomes (e.g. Urinary Drug Screen/Breathalyzer Analysis results, appointment no shows, early drop out, recidivism).

Exploratory Aim: To determine if there are between group differences in neurobehavioral function as a result of treatment modality being received as standard of care in the substance use outpatient setting.

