### **3. Study Design:**

This protocol will recruit approximately 35 Veterans once they enroll in the McGuire VA Medical Center Substance Abuse Treatment Program (SATP) IOP to complete two sessions of questionnaires and neurobehavioral measures, lasting approximately 3 hours in total. Each subject will meet initially with research staff after their SATP intake (conducted as standard of care), but prior to initiating treatment for the first session. Subjects will then meet with research staff again approximately one month later following their completion (or potentially incompletion) of the treatment. Following this meeting, research staff will complete a targeted CPRS medical chart review to collect information on appointment no shows, early termination of services, and results of Urinary Drug Screen (UDS) and Breathalyzer collections, and results of the Beck Depression Scale and Quality of Life Inventory administered during the SATP intake. 90 days following this chart review, a second chart review will occur to collect the same information, if available, for the post-treatment time period, along with information about whether they have re-entered treatment.

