### **4. Methods:**

#### **a. Procedures:**

The study will take place at the Substance Abuse Rehabilitation Program-Intensive Outpatient Program (IOP) of the Richmond VA Medical Center (RICVAMC). To minimize subject burden, consent and the first visit testing procedures will take place in the same visit to RICVAMC if possible. The study entails two visits with study staff. The first visit will include retrieving informed consent, and once enrolled, the completion of several questionnaires (see below). This visit is expected to last 60-90 minutes. The subject will then be scheduled for a follow up visit in to be conducted after he/she completes the intensive outpatient substance use program. This visit will last approximately 2 hours, and will involve questionnaires and desktop performance based tasks (see below)

**CPRS Chart Review.** CPRS records will first be reviewed by research study staff (research assistants) for intake and progress notes pertaining to the entry into IOP. When a Veteran is

identified to be entering the program and is determined to not have legal involvement from examining the intake, the Veteran will be contacted by research staff in a face-to-face encounter in the SATP clinic to explore his/her interest in participating in the current study. If interested, an appointment will be scheduled to meet to complete informed consent and the initial self-report tests. For the purposes of this study, legal involvement will be defined as a current legal issue identified during the clinic screening that mandates the completion of a substance use treatment program.

Once a subject has consented and is confirmed eligible to participate in the protocol, he or she will be assigned a five-digit ID number for this protocol. The subject will be identified by this number on all study forms, questionnaires, and surveys. The file that links a subject's name and other personally-identifiable information to this ID code number will be an electronic excel file on a password-protected virtual drive furnished by VA.

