CPRS will also be used to complete a review following the second visit with subjects to collect information on appointment no shows, early termination of services, results of Urinary Drug Screen (UDS) and Breathalyzer collections, and results of the Beck Depression Inventory and Quality of Life Inventory administered during the SATP intake. 90 days following this chart review, a second chart review will occur to collect the same information, if available, for the post-treatment time period, along with information about whether they have re-entered treatment.

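### Aim 1 asks whether task scores predict adherence, but the Data Analysis section plans no analysis with a task score as predictor, and the tasks come after the in-treatment outcomes

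*Protocol*

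**What the plan says.** Section 1 of the protocol states one main aim and one exploratory aim. Aim 1 asks whether measured function in three domains (motoric impulsivity, decision making, problem solving) "is predictive of treatment success and adherence outcomes". Its examples of such outcomes are "Urinary Drug Screen/Breathalyzer Analysis results, appointment no shows, early drop out, recidivism". The exploratory aim asks whether the same function differs by treatment modality.

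Section 4, Data Analysis, opens with an "independent-group t-test of each of the following continuous dependent variables", or a chi-square test where the variable is categorical. Seven variables follow, numbered 1 to 8 with no item 6. The section then adds a repeated-measures analysis of depression and quality of life, an exploratory look at within-subject BIS-11 change, and lastly "a between-group design comparing the MFP group vs. TAU group". It closes with: "Individual differences in PTSD and anxiety measures and other symptomatology will be included as covariates to account for confounding factors in the analyses".

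On timing, Section 4, Procedures, gives visit one to consent and questionnaires. Of the follow-up visit it says: "This visit will last approximately 2 hours, and will involve questionnaires and desktop performance based tasks". The project timeline puts treatment at Day 0 to 28 and the post-treatment assessment at Day 29 to 35. After visit two the chart is read for "appointment no shows, early termination of services, results of Urinary Drug Screen (UDS) and Breathalyzer collections", among other items. Section 3 adds that, 90 days after that review, "a second chart review will occur to collect the same information, if available, for the post-treatment time period", along with treatment re-entry. The timeline shows this second review at Day 120.

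**The concern.** A predictive aim needs an analysis that relates the predictor to the outcome, and a predictor measured before the outcome. The plan as written has a gap on both counts.

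If the plan is followed literally, one of two things happens. Either the listed tests compare treatment groups, so that only the exploratory aim is tested, or a score taken after treatment is related back to how treatment went and is reported as prediction. In the second case a poor score at Day 29 to 35 may be a result of substance use or drop-out during treatment rather than a sign that foretold it. A reader could not tell which comparison answers the one aim that is not exploratory.

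**Working it through.** The protocol gives no figure to reproduce on this point, so the check sets the sections side by side.

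**Step 1. Role of each listed variable.**

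| Item in the Data Analysis list | Role in Aim 1 | Role in the list |
|---|---|---|
| 1 Drug-free urines | outcome | dependent |
| 2 Retention | outcome | dependent |
| 3 QOLI score | not named | dependent |
| 4 Delay-discounting k | predictor | dependent |
| 5 SSRT | predictor | dependent |
| 7 Emotional Go-NoGo reaction time | predictor | dependent |
| 8 Tower Test errors | predictor | dependent |

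That is 2 + 1 + 4 = 7 variables. Four are scores that Aim 1 treats as predictors, and 0 of 7 are used as predictors. The later analyses in the section (repeated measures, BIS-11 change, MFP versus TAU) do not use a task score as predictor either, and the named covariates are symptom measures.

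**Step 2. Which groups the list compares.** The opening sentence names none. There are two candidates.
- *MFP versus TAU.* All seven variables then make sense as dependent variables. The list serves the exploratory aim, and Aim 1 has no stated analysis.
- *Adherent versus non-adherent.* The hypotheses for the delay-discounting and stop-signal tasks are worded this way. The task comparisons would then bear on Aim 1, but retention and drug-free urines sit in the same list and do not fit as dependent variables.

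The list as a whole fits the first reading better, but the protocol states neither.

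**Step 3. Order in time.** The introduction to the measures and the Visit One list place only questionnaires before treatment. The Tower Test and the three computer tasks stand under Visit Two, and the timeline puts the computer tasks at Day 29 to 35.
- End of treatment to task visit: 29 − 28 = 1 day, up to 35 − 28 = 7 days.
- No-shows, drop-out and screens from Day 0 to 28 therefore all precede the scores.
- Second chart review, if the first is done within the Day 29 to 35 window: 29 + 90 = Day 119, up to 35 + 90 = Day 125. This agrees with the timeline's Day 120 to within a few days.
- The correctly ordered follow-up is therefore about 90 days after the task visit. It covers treatment re-entry and post-treatment UDS/breathalyzer results, where these exist.

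**Step 4. What the sample can carry (context only).** The protocol plans about 35 subjects and states no alpha, power or effect size. Assume two-sided alpha 0.05, 80% power and a continuous outcome. The smallest detectable correlation between score and outcome is tanh[(1.96 + 0.84)/√(n − 3)]:
- n = 35: 0.46
- n = 30: 0.49
- n = 25: 0.54
- n = 20: 0.59

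The finding does not depend on these values. They show why only one or two lead analyses are realistic, above all if post-treatment data are missing for some subjects.

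**The case against.** The strongest reply is that the section describes what the analytic plan includes and does not claim to be complete, so a regression could stand in a statistical analysis plan that is not shown. That is fair for details. For this reason the absence of no-shows and re-entry from the list, and the lack of a working definition of adherence, are not pressed here. It does not answer the main point. The protocol fixes the role of the task scores and the visit at which they are taken, and neither suits the aim it states. A later analysis plan can add a model, but it cannot move the tasks to before treatment.

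A second reply is that pre-treatment predictors do exist: the BIS-11 and BAM are given at visit one with hypotheses about adherence. This is true. But both are self-report, and the protocol's own background says that trait measures often correlate poorly with task measures. They do not fill the gap for Aim 1's task domains.

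A third reply is that the background presents these behaviours as early markers of longer-term benefit, which suits testing after treatment followed by a later chart review. This stands, and it is why the post-visit outcomes are accepted here as correctly ordered.

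A reader might also infer stronger faults that the protocol does not support:
- *No comparison groups are named anywhere.* MFP versus TAU is named for the last analysis. Only the opening list, and the group term in the interaction, are left open.
- *The stated tests contradict the stated covariates.* A t-test or chi-square test cannot carry covariates, but the covariate sentence follows analyses that can, and may refer to those alone.
- *The tests are circular.* This arises only if the groups are defined by adherence, which the protocol does not say.
- *A t-test of task score by adherence runs in the wrong direction and is invalid.* For a binary outcome without adjustment, it examines the same association as using the score as predictor. The fault lies in the timing.

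**Conclusion.** The point holds in two parts. First, the Data Analysis section specifies no analysis in which a task score predicts treatment success or adherence: all four task scores are dependent variables, in a list of 7 that does not name its groups. Second, the tasks follow the whole Day 0 to 28 treatment window, so in-treatment no-shows, drop-out and screens can be associated with the scores but not predicted by them.

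Aim 1 is not beyond rescue, as a reader might conclude. Re-entry and post-treatment screens over roughly 90 days after the task visit come in the right order and are already to be collected. This conclusion assumes that visits and chart reviews keep to the stated schedule, and that the tasks are given only at visit two. Section 3 speaks loosely of neurobehavioral measures across two sessions, but the detailed sections place them at the second visit alone.

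This should be fixed before analysis, because otherwise the only non-exploratory aim is either untested or answered with a retrospective association.

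**What to change.** 1. In Data Analysis, state which groups the t-test/chi-square list compares. If they are MFP and TAU, say that the list serves the exploratory aim.
2. For Aim 1, add one or two regressions chosen in advance, with a task score as predictor and a post-visit outcome as response: treatment re-entry, or UDS/breathalyzer results. Count only results dated after the task visit, since up to 7 days of the post-treatment period may fall before it. Use the PTSD and anxiety covariates already stated where the number of events allows.
3. Narrow the wording of Aim 1 so that *predictive* applies only to outcomes after the task visit. Report associations with in-treatment no-shows, drop-out and screens as retrospective.

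The cost is a rewording of two sections and one or two more models. No visit, measure or chart review is added. The price in content is a more modest claim about in-treatment adherence. Post-treatment screens are promised only where available, so the report should give the number of subjects with data and acknowledge that availability may be selective.

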The VA has an increasing need for brief, efficacious interventions to assist Veterans in reducing alcohol and substance abuse. The emphasis on brief therapies is partly due to VA initiatives and ongoing access concerns that have limited the number of sessions providers are allotted with patients. Additionally, there are significant efforts to roll out and integrate evidence based practices across the VA. This exploratory aim will be an effort to meet the intersection of these demands by examining a brief evidence-informed therapy for substance users in outpatient treatment. The focus of this aim will be to determine whether this treatment results in measurable changes in neurobehavioral performance shown to be aberrant in addiction. These behaviors might serve as *early-indicator proxy markers* for improvement in cognitive domains relevant to addiction, which could in turn result in longer-term benefits of alcohol or drug abstinence.

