**Visit One:**

The following self-report measures (questionnaires) will be administered with paper-and-pencil:

*Brief Addiction Monitor (BAM)* – The BAM is a 17-item self-report questionnaire that assesses the recent occurrence and frequency of various substances, including marijuana, cocaine, stimulants, and opiates. It additionally has items for the rater to respond to recent health (excellent, very good, good, fair, poor), and recent engagement in risky situations or treatment. Lastly, it has several items asking about symptoms of substance use disorder, such as cravings and difficulties related to substance use (Cacciola et al., 2013). We hypothesize subjects with more reported substance use and less engagement in treatment resources will have poorer treatment adherence. This measure will take approximately 10 minutes to complete.

*Barratt Impulsiveness Scale (BIS-11)* - The BIS-11 is a reliable and valid self-report measure of attentional, motor, and non-planning impulsivity composed of 30 items rated on a 4 point Likert scale from rarely/never to almost always/always (Patton, Stanford, & Barratt, 1995). We hypothesize subjects with higher impulsivity will be more likely to have poorer treatment adherence. This measure will take approximately 10 minutes to complete.

*PTSD Checklist 5* - This is a VA-distributed measure of 20 PTSD-related symptoms (each scored from 0-4) that align with DSM-5 PTSD criteria. It is administered in addition to the SCID itself in order to provide a continuous variable of PTSD symptom severity (Bovin et al., 2016). This measure is being used to account for potential confounding symptomology that may lead to treatment adherence issues. This measure will take approximately 10 minutes to complete.

*Beck Anxiety Inventory* - This is a tally of the subject's self-reported experience of 21 different anxiety-related symptoms in the past week-including the day of testing, where each item is rated on a scale from 0-3 (A. T. Beck, Epstein, Brown, & Steer, 1988). This measure is being used to

account for potential confounding symptomology that may lead to treatment adherence issues. This measure will take approximately 10 minutes to complete.

Visit Two:

The following self-report measures (questionnaires) will be administered with paper-and-pencil:

*Barratt Impulsiveness Scale (BIS-11)* – See above for description

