Day -7 – Day -1	
 
- Contact with potential subjects for recruitment during a face to face meeting when they are in the SATP clinic
 
- Consent and pre-treatment baseline assessment
 
	Brief Addiction Monitor (BAM), Barrett Impulsivity Scale-11 (BIS-11), Posttraumatic Checklist-5 (PCL-5), Beck's Anxiety Inventory
Day 0 – Day 28	
 
- Participants engage in either MFP or TAU treatment during their IOP engagement
 
	N/A
Day 29 – Day 35	
 
- Post-treatment assessment
 
- Chart review: treatment engagement (appointment no shows, early drop out) and Breathalyzer/UDS results, results of Beck Depression Inventory and Quality of Life Inventory.
 
	BIS-11, Delay Discounting Task, Stop-Signal Task, Emotional Go-NoGo task, Quality of Life Inventory
Day 120	
 
- Chart Review: recidivism (treatment re-entry) and Breathalyzer/UDS results
 
	N/A

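### The only named substance-use variable is drug-free urines, although alcohol-only Veterans are eligible and breathalyzer results are collected; unless the urine panel detects alcohol, drinking scores as success

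*Protocol*

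**What the plan says.** Aim 1 (Purpose and Objectives) asks whether neurobehavioral function predicts treatment success and adherence. As examples of those outcomes it gives "Urinary Drug Screen/Breathalyzer Analysis results, appointment no shows, early drop out, recidivism". The rationale looks ahead to "longer-term benefits of alcohol or drug abstinence", and the inclusion criteria admit a Veteran with either an alcohol or a substance use disorder.

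Breathalyzer results are collected. Study Design and the chart-review procedures both take "results of Urinary Drug Screen (UDS) and Breathalyzer collections" from the record after the second visit, and again 90 days later where they exist. The timeline table agrees: its Day 29–35 row lists "treatment engagement (appointment no shows, early drop out) and Breathalyzer/UDS results", and its Day 120 row again lists breathalyzer and urine results.

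The Data Analysis section then numbers the dependent variables. The substance-use item is "proportion drug-free urines; 2) retention in program (Chi-Square". The remaining items are quality of life, delay discounting, stop-signal reaction time, Go-NoGo reaction time and Tower Test errors. A later sentence refers to "substance use primary outcomes of symptomology and neurobehavioral measures for problem solving and impulsivity" for the comparison of the Mind Freedom Plan with usual treatment, but names no variable.

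**The concern.** The named variable is narrower than the population and the data collected. It counts urines free of drugs. If the clinic's panel has no alcohol marker, a participant whose only disorder is alcohol use contributes a value at or near 100% whether abstinent or drinking. The breathalyzer results that could tell the two apart are already extracted, but no analysis is named for them.

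Such participants carry no outcome information in the listed variable, and those who relapse count as successes. In a group comparison they pull both means toward 100%. In Aim 1's question they hold the outcome constant whatever the task score, which weakens any true association. With about 35 participants there is little precision to give away.

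**Working it through.** **Text check.**

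| Question | What the protocol gives |
|---|---|
| Who can enroll? | Alcohol or substance use disorder, so alcohol alone suffices (Recruitment, inclusion criteria) |
| What is extracted? | Urine and breathalyzer results, at both chart reviews (Study Design; Methods; timeline table) |
| What is named for analysis? | Drug-free urines only (Data Analysis, item 1) |
| Could self-report fill the gap? | "The BAM is a 17-item self-report questionnaire that assesses the recent occurrence and frequency of various substances", but it is given only at Visit One, before treatment |
| Does the urine panel detect alcohol? | Not stated |

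**Illustration.** The protocol gives no power calculation, SD, alpha, group sizes or alcohol-only share, so there is no figure to reproduce. Apart from the total of about 35, every input below is an assumption.

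- True mean proportion of negative tests: p = 0.75 in one group (n = 17) and 0.50 in the other (n = 18).
- Between-person SD of that proportion: 0.30, so variance 0.09.
- Alcohol-only share s, equal in both groups. These participants never have a positive drug urine.
- Two-sided 5% t-test, 33 df, power from the noncentral t with noncentrality = difference / √(v₁/17 + v₂/18).

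*Listed variable (urine only).* Observed mean = s + (1 − s)p, so the difference is 0.25(1 − s). Variance v = (1 − s)·0.09 + s(1 − s)(1 − p)².

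- s = 0.2: difference 0.20; v = 0.082 and 0.112; SE 0.105; noncentrality 1.90; power 46%.
- s = 0.4: difference 0.15; v = 0.069 and 0.114; SE 0.102; noncentrality 1.47; power 30%.

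*Combined variable (no positive urine or breathalyzer).* Suppose both tests are done at every occasion and the breathalyzer catches a fraction d of drinking occasions. An alcohol-only participant with true proportion x then scores 1 − d(1 − x). The difference is 0.25(1 − s) + 0.25·s·d, and v = (1 − s)·0.09 + s(0.30d)² + s(1 − s)[(1 − d)(1 − p)]².

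- s = 0.2, d = 0.3: difference 0.215; v = 0.0785 and 0.0932; noncentrality 2.17; power 56%.
- s = 0.2, d = 0.5: difference 0.225; v = 0.0790 and 0.0865; noncentrality 2.31; power 61%.
- s = 0.4, d = 0.3: difference 0.180; v = 0.0646 and 0.0866; noncentrality 1.94; power 47%.
- s = 0.4, d = 0.5: difference 0.200; v = 0.0668 and 0.0780; noncentrality 2.20; power 57%.

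| Alcohol-only share | Listed variable | Combined, d = 0.3 to 0.5 |
|---|---|---|
| 20% | 46% | 56–61% |
| 40% | 30% | 47–57% |

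The useful comparison is across each row. With s = 0 the same formula gives 67%, but that would need no alcohol-only participants, or perfect detection of drinking, and neither change proposed below would deliver it.

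**The case against.** Much can be said against reading this as a contradiction.

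- Aim 1 offers its outcomes as examples, and the analysis section says the plan includes the listed tests, which does not make the list exhaustive. Appointment no-shows and recidivism are likewise collected and unlisted, so breathalyzer results are not singled out. This stands. A reader might infer that the protocol has abandoned an Aim 1 outcome or leaves drinking unmeasured. The text does not support that: the results are collected, and nothing rules out analyzing them.
- The list jumps a number: "5) Stop signal reaction time (SSRT) on the stop-signal task; 7) Reaction time in the Emotional Go-NoGo task". A reader might suppose that a breathalyzer item was lost there. Nothing shows that. The gap falls between two computer-task measures, and no consequence follows from it.
- The harm depends on a urine panel that the protocol does not describe. This stands, and the point is conditional on it.
- The construction of an outcome is commonly left to a statistical analysis plan. This holds in part: a rule for occasions with one test could go there. But item 1 does fix a variable, and the phrase about substance-use primary outcomes is too undefined to widen it.
- The illustration models a two-group contrast, which belongs to the Exploratory Aim if the groups are the two treatments. Aim 1 is about prediction, for which no loss has been computed. The near-equal split is also assumed; the Recruitment section gives no allocation ratio. This stands, and it limits the figures to showing direction and rough scale.

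**Conclusion.** The point holds as a conditional one. The sole named substance-use variable does not draw on the breathalyzer data, although alcohol-only Veterans are eligible and those data are extracted twice. If the urine panel has no alcohol marker, drinking in that subgroup scores as success, and both group differences and associations with the neurobehavioral measures are diluted. The direction follows from the scoring. The size in this study is unknown, because it depends on the panel, the alcohol-only share and the testing pattern, none of which the protocol gives. On the stated assumptions the combined variable gains roughly 10 to 15 percentage points of power at a 20% alcohol-only share and 17 to 27 points at 40%. These are not estimates for this trial.

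**What to change.** In Data Analysis, item 1, do one of the following:

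- Replace the variable with the proportion of test occasions with no positive urine or breathalyzer result, and state how an occasion with only one of the two tests counts.
- If the urine panel already includes an alcohol marker, say so there.

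Either takes one or two lines. Breathalyzer results are already extracted at both chart reviews, so no new data field is needed, and replacing the variable adds no test to the list.

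The cost is that recovery is partial. A breathalyzer detects only recent drinking, post-treatment results are taken only where the chart has them, and the protocol states no testing schedule. Single-test occasions may therefore occur, which is why the rule for them should be fixed in advance.

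### The analysis list omits treatment re-entry and no-shows and gives the urine outcome no time window, so it does not clearly cover the only part of Aim 1 that can be prospective

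*Protocol*

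**What the plan says.** Protocol section 1 states Aim 1 as testing whether neurobehavioral function "is predictive of treatment success and adherence outcomes (e.g. Urinary Drug Screen/Breathalyzer Analysis results, appointment no shows, early drop out, recidivism" and so on; the list of outcomes is given as examples.

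Section 4.a and the measure descriptions in 4.b place all performance tasks at the second visit. The project timeline gives the Day 29-35 measures as "BIS-11, Delay Discounting Task, Stop-Signal Task, Emotional Go-NoGo task, Quality of Life Inventory". The Tower Test is missing from that row, but 4.b describes it under Visit Two.

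Chart data are extracted twice. The first review follows Visit 2. Ninety days later, under 4.a, "a second chart review will occur to collect the same information, if available, for the post-treatment time period". Re-entry into treatment is an added item at this second review only. The timeline labels this step, at Day 120, as "Chart Review: recidivism (treatment re-entry) and Breathalyzer/UDS results".

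The Data Analysis section sets t-tests or chi-square tests for "proportion drug-free urines; 2) retention in program (Chi-Square); 3) Quality of life score on the QOLI; 4) Delay discounting constant k", then stop-signal reaction time (item 5), Go-NoGo reaction time (item 7) and Tower Test errors (item 8). There is no item 6. The rest of the section covers depression, quality of life, BIS-11 change, and a comparison of the two therapies on substance use outcomes and neurobehavioral measures.

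**The concern.** The aim, the collection schedule and the analysis do not line up. Recidivism is named in the aim and has a dedicated data collection step, yet neither it nor re-entry appears in the analysis section. No-shows are also named and collected but not analysed. The urine proportion could mean in-program results, post-program results or both.

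The timing makes this more than a gap in a list. A claim that task performance predicts an outcome needs the performance to be measured first. Here the tasks come after treatment, so an association with in-program attendance or urines could equally reflect the effect of recent use, or of having completed or left treatment, on task performance. The outcomes free of that ambiguity are those after Visit 2. If the urine proportion pools both periods, it mixes results from before and after the predictor.

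**Working it through.** No power or sample-size figure is involved. The check is a comparison of the sections, plus date arithmetic.

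**Step 1: aim against schedule against analysis.**

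| Outcome named in Aim 1 (section 1) | When collected (sections 3, 4.a, timeline) | In Data Analysis? |
|---|---|---|
| Urine and breathalyzer results | Both chart reviews | Urines yes (item 1), no time window; breathalyzer not named |
| No-shows | First review; second review if available | No |
| Early drop-out | First review; second review if available | Yes, as retention (item 2) |
| Recidivism (treatment re-entry) | Second review only | No |

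Two of the four named outcomes have a counterpart and two do not. Seven variables are listed, under numbers 1-5, 7 and 8.

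**Step 2: dates.** The first chart review falls with Visit 2 at Day 29-35. Adding 90 days: 29 + 90 = 119 and 35 + 90 = 125, so Day 119-125. This agrees with the timeline's Day 120; the follow-up schedule is consistent.

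**Step 3: order of predictor and outcome.** The program runs Day 0-28 and the tasks are given at Day 29-35.

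- In-program urines, retention and no-shows (Day 0-28) precede the tasks.
- Results between Day 29 and Visit 2 are post-program but still precede the tasks. If Visit 2 is on Day 35, this gap is 35 − 29 = 6 days. A cut at Day 28 would therefore not cleanly separate before from after; the Visit 2 date does.
- Events after Visit 2 follow the tasks. With a review on Day 120 this window is 120 − 35 = 85 to 120 − 29 = 91 days.

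**Step 4: which post-task outcomes have a stated analysis.** Re-entry has none. Post-visit urines may or may not enter item 1. Post-visit breathalyzer results and no-shows are not named. Post-visit early termination, if available, is not clearly part of item 2, which concerns retention in the program.

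BIS-11 is also given at Visit One, so a baseline questionnaire score does precede in-program outcomes. It is a self-report trait measure and does not replace the task measures of problem solving, decision making and motor impulsivity that Aim 1 is about.

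**The case against.** The strongest reply is that the list is not closed. It is introduced as something the plan includes, item 6 is missing, and the outcomes in Aim 1 are examples. A statistical analysis plan, not shown here, could add models and set the urine window. This would carry weight if the protocol had left its outcome variables to a later document. Instead it enumerates them, and the enumeration does not match its own aim. Item 6 may be a drafting loss, but nothing says it was recidivism.

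A second reply is that the independent groups in the t-tests are not named, and that 4.b frames several hypotheses around Veterans who do not adhere. Adherence or re-entry might then be a grouping factor rather than a dependent variable. The text does not exclude this, but it does not say it either, and retention and drug-free urines as dependent variables fit it poorly.

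Some stronger readings are tempting and not supported:

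- That recidivism is the only outcome after the tasks. Urine and breathalyzer results, and no-shows and early termination where available, are also collected at the second review.
- That the follow-up cannot answer Aim 1, or that its 90 days go unused. Re-entry data are still collected, and a urine proportion without a time window may include follow-up urines.

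**Conclusion.** The point stands as a mismatch between Aim 1 and the stated analysis. Treatment re-entry and no-shows, two of the four outcomes the aim names, have no stated analysis, and the period covered by the urine proportion is undefined. Because the tasks are given at Day 29-35, only outcomes after Visit 2 can be predicted prospectively, and the analysis section does not clearly cover them.

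This does not invalidate the study, since the data will exist. It should be corrected because it bears on the main aim and is cheap to repair. The conclusion assumes that the performance tasks are given only at Visit 2. Section 3 speaks loosely of two sessions of questionnaires and neurobehavioral measures, but 4.a, 4.b and the timeline all put the tasks at the second visit.

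**What to change.** In the Data Analysis section:

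1. Name treatment re-entry and post-Visit 2 urine and breathalyzer results as the outcomes of the prospective Aim 1 analysis, with Visit 2 task scores as predictors. Count them from each participant's own Visit 2 date.
2. Report in-program urines, retention and no-shows separately, described as associations with outcomes that precede the tasks.
3. Correct the item numbering, and either restore item 6 or confirm that nothing is missing.

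The cost is protocol wording and one or two further analyses of data already due to be extracted. Dates of re-entry and of each test must be taken from the chart so that events can be placed before or after Visit 2. Few events are likely among about 35 Veterans (the protocol gives no expected re-entry rate), so the results will be imprecise and should be presented as estimates with confidence intervals, not as significance tests alone.
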